#### 7 STATISTICAL METHODOLOGY AND STATISTICAL ANALYSES

#### 7.1 STATISTICAL METHODS

This is a descriptive study, and as such, no statistical testing will be conducted. Analyses will be conducted using Statistical Analysis System (SAS) (version 9.3 or higher). Summary statistics for patient demographics, clinical characteristics, treatment patterns, and patient HCRU will be performed. Continuous variables will be summarized using standard summary statistics such as number of observations (n), mean, median, standard deviation (SD), first and third quartile, minimum and maximum value. Categorical variables will be summarized in frequency tables as counts and proportions of the total study population, and by subgroups where appropriate. The proportion of missing data will be reported for each variable.

Ad hoc population analyses would include stratification by demographic characteristics and presence of Underlying Medical Conditions Associated with Higher Risk for Severe COVID-19.

All patients who fulfill the study eligibility criteria will be included in the data set for analyses.

One interim analysis will be conducted after 3 months of recruitment only if the target sample size is not achieved from Cohort 1 i.e. Cohort 2 is initiated.

#### 7.2 STATISTICAL ANALYSES

Note: Cohort 2 will be included in the study only if the target sample size is not achieved from Cohort 1.

Patients' enrollment will be summarized as shown in *Table Shell 1*.

Primary analysis: To describe the baseline demographic and clinical characteristics, including pre-existing comorbidities, of adult COVID-19 patients who have been prescribed nirmatrelvir, ritonavir treatment.

Patient and disease characteristics will be summarized using descriptive statistics. In terms of sociodemographic characteristics age, gender, ethnicity, education, and employment status will be reported as shown in *Table Shell 2*. Clinical characteristics in terms of weight, height, Body Mass Index (BMI), smoking status, pre-existing comorbidities, duration between pre-existing comorbidities and Index date in months, concomitant medications used to treat comorbidities at index date, most common concomitant medications (Trade name or generic name) for comorbidities, and most common Indication for comorbidities at index date will be reported as shown in *Table shell 3*.

Patient's COVID-19 vaccination history in terms of patient vaccinated/not vaccinated, total numbers of dose, type of vaccine, duration between vaccination and index date will be reported as shown in the *Table shell 4*.

Similarly, data on previous COVID-19 infection will be reported in terms of Number of previous COVID-19 infection, duration between previous infection to the index date, Medication used to treat previous COVID-19 infection as shown in the *Table shell 5*. COVID-19 Positive infection data at index date will be reported in terms of Type of COVID-19 Test (PCR or Antigen test), Result of COVID-19 Test (PCR or Antigen test), result of PCR test only, result of Antigen test only, duration between COVID-19 symptoms onset to index date, variant of COVID-19, medication used to treat the infection as shown in the *Table shell 6*.

Data related to Nirmatrelvir/Ritonavir prescription in terms of specialty of provider total dose of Nirmatrelvir/Ritonavir, in case of "other" dose specified of Nirmatrelvir and Ritonavir (if available), frequency, dispensed amount, type dispensed, days from COVID-19 diagnosis to nirmatrelvir, ritonavir at index date, days from prescription to dispensing (if available), days from COVID 19 symptoms onset to dispensing (if available) and days from COVID 19 symptoms onset to nirmatrelvir, ritonavir prescription (if available) will be summarized in descriptive statistics and reported as shown in the *Table shell 7*.

Data of Patient hospitalization, primary cause of patient hospitalization, length of hospitalization stay, Intensive Care Unit (ICU) admission, length of stay in Intensive Care Unit (ICU), supplemental oxygen use, type of oxygen, vasopressor use, patient intubation, outpatient visits, reason of outpatient visits, Emergency Room visits, and reason of Emergency Room visits at index date will reported as shown in the *Table shell* **8**.

# Secondary analysis: To assess adult COVID-19 patients' HCRU within the 30-day period following nirmatrelvir, ritonavir prescription, including: Overall HCRU in inpatient and outpatient settings.

Healthcare Resource Use (HCRU) data will be summarized using descriptive statistics in terms of patient hospitalization, number of time patient hospitalization, cause of patient hospitalization, length of stay in the hospitalization, Intensive Care Unit (ICU) admission,

PFIZER CONFIDENTIAL CT24-WI-GL03-RF03 2.0 Non-Interventional Statistical Analysis Plan 01-Jun-2020 Page 19 of 42 number of Intensive Care Unit (ICU) admission, length of stay in Intensive Care Unit (ICU), supplemental oxygen use, type of oxygen, vasopressor use, patient intubation, outpatient visits, number of outpatient visits and reason of outpatient visits during the 30 days post index date and reported as shown in the *Table Shell 9*. Further stratification will be performed as described in section 3.2.

COVID-19 PCR and /antigen test result(s), Result(s) by PCR only, Result(s) by antigen test only, duration to COVID-19 negative result(s) by PCR and/antigen tests from the index date will be reported will be reported as shown in the *Table shell 21*.

COVID-19 variant by following stratifications will be reported as shown in the *Table shell 22.1 to 22.7: (if sample size permits)* 

- Age groups: *Table shell 22.1*
- Gender: *Table shell 22.2*
- BMI categories: *Table shell 22.3*
- Smoking status: *Table shell 22.4*
- Previous COVID-19 infection: *Table shell 22.5*
- COVID-19 vaccination history: Table shell 22.6
- Underlying medical conditions: Table shell 22.7

Duration to COVID-19 negative result(s) by following stratifications will be reported as shown in the *Table shell 23.1 to 23.10: (if sample size permits)* 

- Age groups: *Table shell 23.1*
- Gender: *Table shell 23.2*
- BMI categories: *Table shell 23.3*
- Smoking status: *Table shell 23.4*
- Previous COVID-19 infection: *Table shell 23.5*
- COVID-19 vaccination history: *Table shell 23.6*
- Underlying medical conditions: Table shell 23.7
- Medications used to treat COVID-19 in addition to nirmatrelvir, ritonavir: *Table shell 23.8*
- Days from COVID-19 diagnosis to nirmatrelvir, ritonavir index date: *Table shell* 23.9
- Days from prescription to dispensing (*if available*): *Table shell 23.10*

#### 7.3 ADDITIONAL EXPLORATORY ANALYSIS

#### Summary

The following exploratory analysis will be conducted:

- 1. Stratified analysis of Paxlovid prescription at index by demographic and clinical characteristics.
- 2. Stratified analysis of HCRU (Healthcare Resource use) at index date by demographic and clinical characteristics.
- 3. Examine the association between patients' hospitalization due to COVID-19 related reasons at the index date and Covariates\*, using logistic regression model. \**Covariates: Age groups, Gender, BMI categories, smoking status, Pre-existing comorbidities, previous*

#### Statistical analysis description

## 1. "Stratified analysis of Paxlovid prescription at index by demographic and clinical characteristics"

Data related to Nirmatrelvir/Ritonavir prescription in terms of specialty of provider total dose of Nirmatrelvir/Ritonavir, in case of "other" dose specified of Nirmatrelvir and Ritonavir, frequency, dispensed amount, type dispensed, days from COVID-19 diagnosis to nirmatrelvir, ritonavir at index date, days from prescription to dispensing days from COVID-19 symptoms onset to dispensing and days from COVID-19 symptoms onset to nirmatrelvir, ritonavir prescription will be summarized in descriptive statistics by:

- Age groups: 18–49, 50–64, 65–74, ≥75 years
- Gender
- BMI categories:  $(<18.5 = underweight, 18.5-24.9 = normal, 25-29.9 = overweight, \geq 30 = obese).$
- Smoking status.
- Previous COVID-19 infection.
- COVID-19 vaccination history.

These tables will be reported as shown in the table shells 7.1 to 7.6

## 2. "Stratified analysis of HCRU (Healthcare Resource use) at index date by demographic and clinical characteristics"

Data of Patient hospitalization, primary cause of patient hospitalization, length of hospitalization stay, Intensive Care Unit (ICU) admission, length of stay in Intensive Care Unit (ICU), supplemental oxygen use, type of oxygen, vasopressor use, patient intubation, outpatient visits, reason of outpatient visits, Emergency Room visits, and

reason of Emergency Room visits at index date will be summarized in descriptive statistics by:

- Age groups: 18–49, 50–64, 65–74, ≥75 years
- Gender
- BMI categories:  $(<18.5 = underweight, 18.5-24.9 = normal, 25-29.9 = overweight, \geq 30 = obese).$
- Smoking status.
- Previous COVID-19 infection.
- COVID-19 vaccination history. These tables will be reported as shown in the **table shells 8.1 to 8.6**.

## 3. "Examine the relationship between patients' hospitalization due to COVID-19 related reasons and various demographic and clinical factors at the index date."

We will be utilizing both univariate and multivariate binomial logistic regression to examine the association between patients' hospitalization due to COVID-19 at the index date and demographic and clinical factors mentioned below (covariates). All p-values will be reported as two-sided, and statistical significance will be determined at 0.05 alpha level. Separate univariate binary logistic regression model will be conducted for each covariate listed below and only covariates which will be found significant will be included in the Multivariate model along with clinically significant covariates (e.g BMI, Previous comorbidity status etc.). No interaction terms will be included in the model.

The following binary logistic regression equation will be used to model the relationship:

 $log(odds) = \beta_0 + \beta_1 X_1 + \beta_2 X_2 + \dots + \beta_n * X_n$ 

Where:

- log(odds) represents the logarithm of the odds of the patients' hospitalization due to COVID-19
- $\beta_0$  is the intercept or constant term.
- β1, β2, ..., βn are the coefficients associated with the independent variables (covariates) X1, X2, ..., Xn.
- X1, X2, ..., Xn are the values of the independent variables (Covariates)

Here,

**Outcome variable (Dependent variable):** patients' hospitalization due to COVID-19 related at index date (Yes=1/No\*\*=0).

\*\*No: No will include both "patients who had no hospitalization" as well as "patients with hospitalization due to non-COVID-19 related reasons".

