#### Figure 1. Study Design

#### 3.1.1 Study population

Data will be collected for all eligible adult COVID-19 patients who have been prescribed nirmatrelvir, ritonavir across 3 selected sites in KSA which are National Guard Hospital-Riyadh, King Faisal Specialist Hospital-Riyadh and King Faisal Specialist Hospital-Jeddah. These 3 healthcare centers are the largest COVID-19 care providers in KSA representing the majority of COVID-19 patients who have been prescribed nirmatrelvir, ritonavir at the national level. In addition, these three healthcare centers have the same guidelines for treatment and management of patients with COVID-19.

The selected sites with well-established clinical research infrastructures, are situated in the major cities of KSA, where COVID-19 patients are most prevalent. They provide medical attention to any COVID-19 patient and provide healthcare to complicated patients, including immunocompromised patients.

These facilities also maintain patient records and have access to electronic medical records for patient data retrieval.

The minimum target sample size is 250 patients. Patient eligibility will be assessed at patient index date. Patients in Cohort 1 will be identified during a 15-month lookback period prior to the date of site initiation, and patients in Cohort 2 will be identified

PFIZER CONFIDENTIAL CT24-WI-GL03-RF03 2.0 Non-Interventional Statistical Analysis Plan 01-Jun-2020 Page 11 of 42 following the date of site initiation if the minimum target sample size for the study is not achieved from Cohort 1.

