Days from COVID 19 symptoms onset to nirmatrelvir, ritonavir prescription (Categories)	Nirmatrelvir, ritonavir prescription data	At index date	Days from COVID 19 symptoms onset to nirmatrelvir, ritonavir prescription will be categorized as: • 0-2 days • 3-5 days • $\geq 6$ days
Patient hospitalization	HCRU data	At index date	Patient hospitalization will be reported as: • Yes • No
Cause (Patient hospitalization)	HCRU data	At index date	Cause of patient hospitalization will be reported as (if available); • COVID-19 related • Non COVID-19 related
Outpatient setting	HCRU data	At index date	Outpatient setting will be defined if answer "No" to question "Patients hospitalization"
Length of Stay (Days) (Patient hospitalization)	HCRU data	At index date	Length of patients stay in hospitalization will be captured in days
Intensive Care Unit (ICU) admission	HCRU data	At index date	Intensive Care Unit (ICU) admission will be reported as: • Yes • No

Variables	Role	Time point(s)	Operational definition
Length of Stay (Days)	HCRU data	At index date	Length of patients in Intensive
(ICU)			Care Unit (ICU) will be captured
			in days
Supplemental oxygen	HCRU data	At index date	Use of supplemental oxygen will
			be reported as:
			• Yes
			• No
Type of Supplemental	HCRU data	At index date	Type of supplemental oxygen
oxygen			use will be reported as:
			Oxygen mask
			Nasal prongs
			NIMV
			HFNC
			• IMV
			• ECMO
Vasopressor use	HCRU data	At index date	Use of Vasopressor will be
· ···· · · · · · · · · · · · · · · · ·			reported as:
			• Yes
			• No
Patient intubation	HCRU data	At index date	Patient intubation data be
i unent intuoution	fierce duiu	The match dute	reported as:
			• Yes
			• No
Outpatient visits	HCRU data	At index date	Outpatient visits data be reported
Outputient visits	Here dutu	The mack dute	as:
			• Yes
			• No
Cause	HCRU data	At index date	Cause of Outpatient visits will be
(Outpatient visits)		Tri maex date	reported as (if available).
(Outputient visits)			COVID-19 related
			Non COVID-19 related
ER Visits	HCRU data	At index date	ER visits data be reported as:
LIX VISIUS		At much date	Yes
			• No
Reason	HCRU data	At index date	Reason of ER visits will be
(ER Visits)	IICKU uata	At much uate	reported as (if available);
(LIX VISIIS)			
 
COVID-19 related
 

			
 
Non COVID-19 related
 

Detiont hospitalization		During the 20	
Patient hospitalization	HCRU data	During the 30 day of post-	Patient hospitalization will be

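### The logistic model's 'No' group pools patients hospitalised for non-COVID reasons with patients not in hospital, which may attenuate the odds ratios for covariates that also predict non-COVID admission

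*SAP*

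**What the plan says.** SAP 7.3, item 3, plans univariate and multivariable logistic regression "to examine the association between patients' hospitalization due to COVID-19 at the index date and demographic and clinical factors". The outcome is COVID-19-related hospitalisation at index, yes (1) or no (0). A footnote to the outcome states that the 0 group contains both patients with no hospitalisation and "patients with hospitalization due to non-COVID-19 related reasons".

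Tests are two-sided and "statistical significance will be determined at 0.05 alpha level". For the multivariable model, "only covariates which will be found significant will be included in the Multivariate model", alongside covariates judged clinically important, of which BMI and comorbidity status are named as examples. The covariates are age group, gender, BMI category, smoking, pre-existing comorbidity, previous infection and vaccination.

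Non-COVID inpatients can enter the analysis. SAP 3.1.3 sets no exclusion criteria. SAP 3.1.1 says the sites "provide healthcare to complicated patients, including immunocompromised patients". The index-date cause field in SAP Annex 1 (Table 2) has a non-COVID level, completed when the cause is available. The only regression outputs in SAP section 9 are Shells 24 (univariate binary models) and 24.1 (multivariable binary model). SAP section 8 does not list the mixed comparator as a limitation.

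**The concern.** A patient already in hospital for another reason differs from one managed outside hospital. If such patients tend to be older or to have more comorbidity, they bring into the comparison group the same factors whose association with COVID-19 admission is being estimated. The odds ratio then reflects two things at once: how the factor relates to COVID-19 admission, and how many incidental inpatients each site contributed. Readers are likely to take the results as risk factors for COVID-19 admission among treated patients. A weakened association may also miss the univariate significance screen and so drop out of the multivariable model.

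**Working it through.** The documents give no event rate, odds ratio or share of non-COVID inpatients, so there is no planned figure to reproduce. From the SAP come the outcome coding, the two-sided 0.05 level and the minimum of 250 patients. Every share and prevalence below is an assumption.

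**1. Age 75 or over, treated as one binary covariate** (the SAP uses age groups). Assume 15% of the sample are COVID-19 admissions, with age ≥75 in 30% of these, 15% of non-hospitalised patients and 40% of non-COVID inpatients. Let s be the share of non-COVID inpatients in the whole sample.

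- Against non-hospitalised patients only: (0.30/0.70)/(0.15/0.85) = 0.4286/0.1765 = 2.43.
- Under the SAP coding, prevalence in the 0 group is p = [(0.85 − s) × 0.15 + s × 0.40]/0.85, and OR = 0.4286/[p/(1 − p)].

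| s | p | odds in 0 group | OR as coded |
|---|---|---|---|
| 2% | 0.1325/0.85 = 0.156 | 0.185 | 2.32 |
| 5% | 0.1400/0.85 = 0.165 | 0.197 | 2.17 |
| 10% | 0.1525/0.85 = 0.179 | 0.219 | 1.96 |
| 20% | 0.1775/0.85 = 0.209 | 0.264 | 1.62 |

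**2. Comorbidity**, assumed in 82%, 60% and 95% of the same three groups. The OR against non-hospitalised patients is (0.82/0.18)/(0.60/0.40) = 3.04. As coded it is 2.93, 2.79, 2.55 and 2.12 at s = 2%, 5%, 10% and 20%. This is the more extreme example: the implied OR for non-COVID admission is (0.95/0.05)/(0.60/0.40) = 12.7. For age it is (0.40/0.60)/(0.15/0.85) = 3.8.

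**3. Direction.** For covariate level x (0 or 1), let b_x and c_x be the probabilities of non-COVID hospitalisation and of no hospitalisation. Then

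OR as coded = OR against non-hospitalised × (1 + b0/c0)/(1 + b1/c1).

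An OR above 1 shrinks only if the covariate raises the odds of non-COVID hospitalisation against no hospitalisation. With a covariate split 50:50, 20% COVID-19 admissions and an OR of 2.00 against non-hospitalised patients, the OR as coded is:

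| Non-COVID share | covariate OR for non-COVID admission 0.5 | 1 | 2 | 3 | 5 |
|---|---|---|---|---|---|
| 5% | 2.08 | 2.00 | 1.92 | 1.87 | 1.83 |
| 10% | 2.17 | 2.00 | 1.84 | 1.75 | 1.67 |
| 20% | 2.36 | 2.00 | 1.68 | 1.53 | 1.37 |

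**4. Effect on the 0.05 screen at 250 patients.** In the step 3 setting with a covariate OR of 3, power is 0.42 as coded against 0.57 with non-COVID inpatients removed (10% share), and 0.26 against 0.56 (20% share). For the age example at s = 10%, by Wald approximation:

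- Removed (37.5 cases, 187.5 comparators): SE of the log OR = √(1/11.25 + 1/26.25 + 1/28.125 + 1/159.375) = 0.411; z = 0.887/0.411 = 2.16; power 0.58.
- As coded (37.5 and 212.5): SE = √(1/11.25 + 1/26.25 + 1/38.125 + 1/174.375) = 0.399; z = 0.673/0.399 = 1.69; power 0.39.

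**5. Can the sign reverse?** That needs (1 + b1/c1)/(1 + b0/c0) to exceed the OR against non-hospitalised patients. For an OR of 2 with b0/c0 = 0.10, b1/c1 must exceed 2 × 1.10 − 1 = 1.2. Then 1.2/2.2 = 55% of the exposed 0 group would be non-COVID inpatients, a covariate OR of 12. Over 10–30% COVID-19 admissions, 2–30% non-COVID inpatients and covariate ORs of 0.5 to 5, reversal occurred only for an OR of 1.5, with 20–30% non-COVID inpatients and a covariate OR of 3 to 5. It never occurred for an OR of 2 or 3.

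**The case against.** The strongest reply is that COVID-19-related hospitalisation against all other treated patients is a defined and openly disclosed contrast. The SAP never names non-hospitalised patients as the intended comparator, so the coding is a choice of contrast and not an error. That stands, and it is why the planned model need not be replaced. Dropping patients from the main model would also conflict with SAP section 6, which assigns every analysis to the Full Analysis Set.

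Shell 8 already reports hospitalisation and its primary cause at index, and Shells 8.1 to 8.6 break this down by every model covariate except comorbidity. This also stands: much of the make-up of the 0 group will be visible. These tables are descriptive, however. They give no adjusted odds ratio against non-hospitalised patients, and nothing by comorbidity.

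On the screen, comorbidity and BMI are named as examples of covariates that can enter on clinical grounds, and Shell 24 reports every univariate result. The screening worry therefore applies mainly to age and the other covariates not named.

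A reader might infer that the coding pulls all the odds ratios towards the null, or past it. The documents do not support that. They give neither the share of non-COVID inpatients nor its relation to any covariate. The description of the sites' case mix covers all their patients and yields no count. For gender, smoking, vaccination or previous infection the shift could be nil or away from the null.

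**Conclusion.** The point holds in a limited form. The 0 group is mixed, no planned model separates its parts, and the odds ratios for covariates that also predict non-COVID admission may be attenuated relative to a comparison with non-hospitalised patients. Age and comorbidity are plausible candidates, though the documents do not establish this for either. On the assumed inputs the loss for age ≥75 runs from slight (2.43 to 2.32 at a 2% share) to material (2.43 to 1.62 at 20%). Reversal of an association needs extreme inputs and appears in neither worked example. The analysis is exploratory and the study's descriptive objectives are untouched, so this is a cheap improvement.

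**What to change.** Keep the planned binary model on the Full Analysis Set. Add one of the following to SAP 7.3, item 3, and to Shells 24 and 24.1:

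- a three-level multinomial logistic model (COVID-19 admission, non-COVID admission, not hospitalised) with not hospitalised as reference; or
- a sensitivity analysis of the binary model that leaves out non-COVID inpatients.

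In either case show the number of patients in each outcome category beside the odds ratios, and say how a hospitalised patient with no recorded cause is classified, because the cause field is completed only when available.

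The cost is SAP wording, one model option or filter, and extra table columns. No new data are needed. The multinomial model keeps every patient whose outcome can be classified but will have sparse cells if non-COVID inpatients are few. The sensitivity analysis has a slightly smaller comparison group; in the age example the SE of the log OR is 0.411 against 0.399.

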#### **Covariates (Independent variables):**

- Age groups (Reference group: 18-29 Year)
- Gender (Reference group: Female)
- BMI categories (Reference group: Normal)
- Smoking status (Reference group: Never smoke)
- Pre-existing comorbidities (Yes/No, Reference group: No)
- Previous COVID-19 infection (Yes/No, Reference group: No)
- COVID-19 vaccination history (Yes/No, Reference group: No)

The results will be presented in the terms of odd ratio (by exponentiating the logistic regression coefficient) and corresponding 95% CI. "p-values" and "confidence intervals (CIs)" will be obtained using statistical methods such as maximum likelihood estimation (MLE) or Wald tests.

These tables will be reported as shown in the table shells 24 to 24.1.

